## 19.4 Analysis of the Primary Efficacy Endpoint

The primary efficacy endpoint will be based on a success (Yes/No) variable, indicating if a subject is no longer requiring supplemental oxygen, for at least 24 hours by study Day 14 (patient death or subsequent requirement of supplemental oxygen or lost to follow-up through Day 42 will be regarded as a failure for the primary efficacy endpoint). Any subject reported as not requiring supplemental oxygen on any given study day will be counted as a subject who has not required oxygen for at least 24 hours, based on the instructions to sites to enter the highest oxygen requirement for each study day. Subjects who are discharged from hospital on supplemental oxygen are expected to be followed up by the study site daily and will be considered a success only if for any given study day, the highest supplemental oxygen requirement is zero.

If a patient initiates a new investigational therapy on a different formal clinical protocol for COVID-19 within 14 days of randomization, the patient will be followed for true outcomes in the primary analysis but in a sensitivity analysis the data under the new therapy will not be included.

An early discontinuation of study before the subject has reached success (e.g. loss to follow up) thus preventing continued follow-up for success by Day 14, will be considered as missing data and will be counted as failure for the primary analysis. Sensitivity analysis using time to event method will be performed censoring these cases at the latest informative time.

The number and percentages of subjects achieving success (as defined above) will be tabulated per treatment group. A 95% confidence interval will be constructed for each proportion. A Cochran Mantel-Haenzel (CMH) test will compare the proportion of success between the two groups, using the study stratification factors used for randomization, and a corresponding stratified risk difference estimate will be presented with 95% confidence interval.

The significance level for this test will be two-sided 5%.

The primary analysis will be based on the modified Intent to treat population (mITT) as defined in Section 19.3.

Sensitivity and supportive analyses for the primary endpoint analysis will be defined and detailed in the statistical analysis plan. These will address at least the following aspects:

- Negation of achieved Day 14 success by a post-day 14 failure event: in a sensitivity analysis, events occurring after day 14 will not impact day 14 success.
- Negation of achieved Day 14 success by any post-success failure: an analysis of endpoint targeting achieving any success will be performed.
- Missing data due to early discontinuation of follow-up before achieving success (prior to day 14): the primary endpoint analysis imputed these cases as Failures, however in this sensitivity analysis, these cases will be handled via censoring, using time to event methodology. Kaplan-Meier method will be used to estimate cumulative incidence of success at day 14. In this analysis death will be censored at 14 days.
- Joining a different clinical trial prior to day 14 while patients do not withdraw consent from being followed up under ABC-201 protocol: a sensitivity analysis will be performed where data collected during the patient participation in another clinical trial are not included.
- A sensitivity analysis of the primary analysis using the subset of patients in the mITT population regardless of meeting inclusion criteria #3 prior to first dose of study drug.
- PP analysis: Criteria for PP protocol will be based on inclusion and exclusion criteria and protocol violations during the study and that confound the interpretation of analyses. Patients who do not meet PP requirement will be defined blindly before database lock.
- To account for the possibility of errors in values of stratification factors used for randomization, the primary analysis will supportively be repeated using the correct values.
- Difference between the treatment and control groups when controlling for possible imbalance in important baseline factors will be analysed by evaluating a multiple logistic regression model. The list of baseline variables will be finalized in the SAP, prior to database lock.
- To understand the possible impact of any initiation of allowed post-randomization effective anti-COVID 19 SOC treatments, descriptive statistics of such usage (frequency and timing of initiation) will be presented for each group.
- The distribution of patient's baseline SoC regimen will be summarized and presented by group. Further, opaganib treatment effect will be assessed to confirm comparability of effect across these strata.

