Justification for Opaganib, Population, Study Design, Primary Endpoint	
The population to be enrolled in this study will have severe COVID-19 infection, be hospitalized and require supplemental oxygen to treat hypoxemia, with or without an increased work of breathing. Data from the recently completed Phase 2a study in the US suggest that opaganib may be beneficial in this population by reducing the need for supplemental oxygen and accelerating the time to discharge from the hospital.
 
As the primary objective of opaganib therapy is to improve and/or stabilize the clinical status of the patient, the primary analysis is based on the proportion of patients who no longer need supplemental oxygen by Day 14 (end of treatment). This outcome will be considered a treatment success. The primary endpoint is consistent with achieving a score of 3 or better (0-3, inclusive) on the WHO Ordinal Scale for Clinical Improvement by Day 14 of treatment.
 
The duration of treatment is 14 days, aligning with approved anti-viral treatment regimens for COVID-19, such as remdesivir.

Primary Objective	To evaluate the proportion of patients no longer requiring supplemental oxygen for at least 24 hours by Day 14
Secondary Objectives	
 
1) To evaluate change on the WHO Ordinal Scale for Clinical Improvement
 
2) To evaluate the time to recovery defined by improvement to a score of 3 or less on the WHO Ordinal Scale for Clinical Improvement
 
3) To evaluate the time to low oxygen flow via nasal cannula e.g. from high oxygen flow via nasal cannula or positive pressure ventilation at baseline
 
4) To evaluate time to discharge from the hospital
 
5) To evaluate the proportion of patients requiring intubation and mechanical ventilation by Day 42
 
6) To evaluate the time to two consecutive negative swabs for SARS-CoV-2 by PCR
 
7) To evaluate the proportion of patients with two consecutive negative swabs for SARS-CoV-2 by PCR at Day 14
 
8) To evaluate the proportion of patients, with at least one measurement of fever at baseline (defined as temperature <math>>38.0\text{ C}</math> [100.4 F]), who are afebrile (defined as temperature <math><37.2\text{C}</math> [99 F]) at Day 14
 
9) To evaluate mortality 28 and 42 days post-baseline
 

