Statistical Methods	
The primary efficacy endpoint will be based on a success (Yes/No) variable, indicating if a subject is no longer requiring supplemental oxygen, for at least 24 hours by study Day 14 (patient death or subsequent requirement of supplemental oxygen or lost to follow-up through Day 42 will be regarded as failure for the primary efficacy endpoint). Any subject reported as not requiring supplemental oxygen on any given study day will be counted as a subject who has not required oxygen for at least 24 hours, based on the instructions to sites to enter the highest oxygen requirement for each study day. Subjects who are discharged from hospital on supplemental oxygen are expected to be followed up by the study site daily and will be considered a success only if for any given study day, the highest supplemental oxygen requirement is zero. By definition, death before day 14 will be regarded as a failure, even if prior room air has been achieved. If a patient initiates a new investigational therapy on a different formal clinical protocol for COVID-19 within 14 days of randomization, the patient will be followed for true outcomes in the primary analysis but be censored at the time that the new therapy was initiated in a sensitivity analysis.
 
If a subject discontinues the study prematurely before reaching success, prior to Day 14, they will be counted as a failure for the primary analysis. Sensitivity analysis using time to event method will be performed censoring these cases at the latest informative time.
 
The number and percentages of subjects achieving success (as defined above) will be tabulated per treatment group. A 95% confidence interval will be constructed for each proportion. A Cochran Mantel-Haenzel (CMH) test will compare the proportion of success between the two groups, using the study stratification factors used for randomization, and a corresponding stratified risk difference estimate will be presented with 95% confidence interval.
 
The significance level for this test will be two-sided 5%. The primary analysis will be based on the modified Intent to treat population (mITT analysis set) which consists of all patients that were randomized and treated with at least one dose of study drug and who met entry criteria #3 (The patient requires, at baseline, high flow supplemental oxygen or positive pressure ventilation, or is receiving oxygen via non-rebreather mask or reservoir mask, capable of delivering high concentrations of oxygen. Patients who require mechanical ventilation or no longer require supplemental oxygen prior to receiving the first dose of study drug will not be included in the mITT analysis set.

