## 15 STUDY ENDPOINTS

### 15.1 Primary

The percentage of patients no longer requiring supplemental oxygen for at least 24 hours by Day 14

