### 19.1 Sample Size Considerations

It is planned to randomize approximately 464 eligible patients into the double-blind treatment phase, to receive either opaganib added to standard of care (n=232), or matching placebo added to standard of care (n=232). The sample size calculation was based on powering the study with respect to the primary analysis of the primary efficacy endpoint of proportions of patients no longer requiring supplemental oxygen for at least 24 hours by Day 14 (refer to Section 15.1). It was assumed that the treatment success rate at 14 days in the control arm would be 40% and that opaganib is expected to provide absolute 15% increase of this rate, to a success rate of 55%. A total of 464 subjects provides 90% power to detect the assumed difference in success rate, using chi square test, at a two-sided  $\alpha=0.05$  level of significance. This sample size calculation takes into account a planned non-binding futility analysis to be performed after at least 135 patients in the study have been evaluated for the primary endpoint.

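### The primary endpoint and its 40%/55% success rates are set at Day 14, but the variable tested also fails a Day-14 success for death, renewed oxygen or mere loss to follow-up through Day 42

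*Protocol*

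**What the plan says.** Several places fix the endpoint at Day 14 and name no later condition:

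- Section 15.1 defines it as "The percentage of patients no longer requiring supplemental oxygen for at least 24 hours by Day 14"; the objective in 9.1 uses the same time frame.
- The synopsis justification says "the primary analysis is based on the proportion of patients who no longer need supplemental oxygen by Day 14 (end of treatment").
- Section 19.1 powers the trial on "proportions of patients no longer requiring supplemental oxygen for at least 24 hours by Day 14 (refer to Section 15.1"), with assumed success at 14 days of 40% on control and 55% on opaganib.

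Two places define the analysed variable differently. Section 19.4 adds in a parenthesis that "patient death or subsequent requirement of supplemental oxygen or lost to follow-up through Day 42 will be regarded as a failure". The synopsis (Statistical Methods) has the same rule, ending "lost to follow-up through Day 42 will be regarded as failure for the primary efficacy endpoint".

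Both places also treat early discontinuation separately, and both limit that rule to patients who have not yet succeeded. Section 19.4: "An early discontinuation of study before the subject has reached success (e.g. loss to follow up) thus preventing continued follow-up". Synopsis: "If a subject discontinues the study prematurely before reaching success, prior to Day 14, they will be counted as a failure". Loss after a success is therefore governed only by the parenthesis, which gives no reason for it.

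The schedule (Section 5, footnotes 1 and 12) has daily telephone assessments of discharged patients until Day 14, then one contact at Day 42, in person or by telephone. Section 19.4 lists a sensitivity analysis in which events after Day 14 do not affect Day-14 success, and another that counts any success ever achieved.

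**The concern.** Two things do not fit together.

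First, a patient can meet 15.1 and be a failure in 19.4. The power statement in 19.1 refers to 15.1 and to rates at 14 days, so on its face it describes an endpoint with a higher success rate than the one tested.

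Second, the three reasons for reversal differ in kind. Death and renewed oxygen are observed outcomes, and counting them asks whether recovery lasted. Loss to follow-up says nothing about the patient. The protocol's explanation for counting loss as failure is that it prevents observation of success by Day 14. That explanation cannot apply once success at Day 14 has been recorded. For a discharged patient, one missed Day-42 contact could reverse an observed result.

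The primary test also gates every secondary endpoint (19.7). Equal loss would shrink the difference. Unequal loss could move it either way.

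**Working it through.** **Inputs.** From 19.1: 40% v 55%, 232 per arm, two-sided 0.05, chi-square test, 90% power. Let l be the share of Day-14 successes lost by Day 42. The documents give no value, so every l below is an assumption. The calculation is unstratified and treats all 464 patients as analysed.

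**Formulas** (pooled variance, no continuity correction; p̄ is the mean of p1 and p2, d = p2 − p1):

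- n per arm = [1.960·√(2p̄(1−p̄)) + 1.2816·√(p1(1−p1)+p2(1−p2))]² / d²
- power = Φ{[d − 1.960·√(2p̄(1−p̄)/n)] / √([p1(1−p1)+p2(1−p2)]/n)}

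**The plan's own figure.** n = [1.960·√0.49875 + 1.2816·√0.4875]² / 0.15² = 230.8, so 231 per arm and 462 in total, against 464 stated. At 232 per arm, (0.15 − 1.960 × 0.04637) / 0.04584 = 1.290, giving power 90.1%. The stated size reproduces from the Day-14 rates with no allowance for later loss.

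**Patients at risk of reversal.** Expected successes are 232 × 0.40 + 232 × 0.55 = 92.8 + 127.6 = 220.4. Loss of 1%, 2% or 5% converts about 2, 4 or 11 of them.

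**Power when each rate is multiplied by (1 − l):**

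| Loss among successes, placebo / opaganib | Rates tested | Difference (points) | Power |
|---|---|---|---|
| 0 / 0 | 40.0% v 55.0% | 15.0 | 90.1% |
| 1% / 1% | 39.6% v 54.45% | 14.85 | 89.6% |
| 2% / 2% | 39.2% v 53.9% | 14.7 | 89.0% |
| 5% / 5% | 38.0% v 52.25% | 14.25 | 87.2% |
| 2% / 4% | 39.2% v 52.8% | 13.6 | 83.8% |
| 4% / 2% | 38.4% v 53.9% | 15.5 | 92.0% |
| 5% / 10% | 38.0% v 49.5% | 11.5 | 70.6% |
| 10% / 5% | 36.0% v 52.25% | 16.25 | 94.4% |

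For the 2% / 4% row: (0.136 − 1.960 × 0.04628) / 0.04584 = 0.988, and Φ = 83.8%.

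**No true effect** (47.5% in both arms, the mean of 40% and 55%). Loss of 2% in one arm and 4% in the other gives 46.55% v 45.60%, a difference of 0.95 points, and two-sided rejection of 5.5%. Loss of 5% and 10% gives 45.1% v 42.75%, 2.4 points, and 8.1%.

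**The case against.** The strongest reply is that 9.1 and 15.1 are one-line labels and that 19.4 and the synopsis, which define the variable, agree with each other. The rule is plainly deliberate, because 19.4 itself lists reversal of a Day-14 success by later failure as something to examine in a sensitivity analysis. Section 19.1 says it powers the primary analysis of the primary endpoint, so 40% and 55% may already be rates under the 19.4 rule. If so, planned power is unaffected.

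The reply goes further. If reversal by death or oxygen use through Day 42 is kept, the durable outcome of a patient lost after Day 14 is unknown. Counting that patient as a success takes the favourable case, and counting failure is the conservative choice. The trial is double-blind, the Day-42 contact can be by telephone, and intubation and mortality need follow-up to Day 42 anyway, so marked imbalance in loss has no support in the documents.

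Much of this stands. It rules out two stronger readings that a reader might infer. One is that the trial is underpowered or 464 is wrong: 464 is right for the Day-14 rates, and the protocol does not exclude that those rates allow for reversals. The other is that the rule inflates the false-positive rate: that needs unequal loss, which is assumed here and not documented.

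The reply does not remove the mismatch. Section 19.1 refers to 15.1 and to success at 14 days, and says nothing of Day 42. The sensitivity analyses drop death and oxygen use together with loss, so neither isolates loss. It is also unclear whether loss is an event in the one that sets aside later events.

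**Conclusion.** The point holds as a mismatch between the stated and the analysed endpoint, with one component, loss alone, that overrides an observed value for a non-clinical reason in the gating test. It should be fixed, but the likely size is modest: about 0.5 to 3 power points for equal loss of 1% to 5% among successes. Larger effects need markedly unequal loss. All these figures rest on assumed loss rates and on 40%/55% not already including Day-42 reversals.

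It would go too far to call reversal by death or documented renewed oxygen an error; that is a defensible durability criterion. What is missing there is consistency, since 9.1, 15.1 and 19.1 do not mention it.

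A related consequence concerns the futility look. Section 19.1 speaks of at least 135 patients evaluated for the primary endpoint, while the synopsis and 19.8 use the Day-14 evaluation of about 135. Under the 19.4 definition, a patient who has only reached Day 14 as a success has not yet been fully evaluated.

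**What to change.** 1. Make 9.1, 15.1, 19.1, 19.4 and the synopsis state one primary endpoint. If death or documented oxygen use through Day 42 is to reverse success, say so in all of them.
2. In the primary analysis, keep the documented Day-14 status (off oxygen at the Day-14 contact) for patients who are only lost after Day 14. Prespecify loss counted as failure as a sensitivity analysis that changes nothing else. Loss before Day 14 remains a failure.
3. State in 19.1 which definition 40% and 55% refer to, and restate the power if it is not the one analysed.
4. Use the 19.8 trigger in 19.1 and state that the futility look uses Day-14 status, since Day-42 status will not be known for all of those patients.

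The cost is wording plus the ethics review that any protocol revision needs (18.2.6); no added patients, visits or data. The downside is a slightly less conservative primary analysis, because an unseen relapse or death after Day 14 would count as success. The sensitivity analysis in item 2 shows how far the result depends on that. The change should be made before unblinding.

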## 19.5 Analysis of the Secondary Efficacy Endpoints

In general, unless otherwise specified in the SAP, binary endpoints where event of interest is of improvement/recovery type by a certain time frame (such as the percentage of patients with  $\geq 2$  category improvement on the WHO Ordinal Scale for Clinical Improvement by Day 14, secondary endpoints #1) will be defined using the following rules: a binary success variable (Yes/No) will indicate if the subject achieved the success of interest within specified timeframe, or not. A recorded failure (within timeframe) after success has been achieved, will be followed-up for re-achieving of success of interest - at the target timeframe. Comparison of these endpoints between treatment groups will employ similar methods as those specified for the primary endpoint. In case there are subjects who discontinue the study before achieving success and before timeframe ending, the cumulative incidence probabilities at desired time-point will be estimated using time to event analysis, censoring these subjects at last valid observation date. In this analysis, death before event of interest will be censored at timeframe end, thus taking the highest unfavorable possible outcome for the endpoint.

For the comparison of percent of patients requiring intubation and mechanical ventilation by day 42, this endpoint is aimed to be assessed as a binary endpoint analysis, unless there are subjects who discontinue the study before meeting event of interest. Otherwise, cumulative incidence probabilities at day 42 time-point will be estimated using time to event analysis, censoring these subjects at last valid observation date. Death prior to experiencing this progression-type of event will be handled via censoring at date of death. As mortality is distinct secondary endpoint, this approach to handling death would allow assessing the effect of opaganib specifically on this event. Sensitivity analysis will estimate cumulative incidence using the nonparametric Aalen-Johansen estimator, where death is a competing event.

Time to event endpoints will be calculated as the number of days from study day 1 until the event of interest or last valid observation time, whichever occurs first (within endpoint timeframe). A patient for whom event of interest will not be observed will be regarded as right censored. Unless otherwise specified in the SAP, the time frame for primary analysis of these endpoints is from Day 1 until Day 14. Time to discharge from hospital will be using end of Day 14 of treatment as end-of-time frame. When event of interest is of Improvement/Recovery type (such as time to recovery), death within the timeframe for each endpoint, will be addressed corresponding to the highest unfavorable possible outcome for the endpoint, which is censoring at the end of time frame.

Time to event endpoints will be compared using the stratified Log-rank test and the stratified Cox proportional hazards regression model will be used to estimate the hazard ratio (HR) along with 95% confidence interval, comparing opaganib versus control group. Kaplan-Meier plot by treatment arm will be presented and cumulative incidence of events of interest will be estimated along with 95% confidence interval for each group at several time points within timeframe.

Mortality endpoints will be defined per subject as a binary variables indicating if a subject had died by target times (28 and 42) days from first dose date. These binary endpoints will be analyzed using the same methods specified for the binary endpoints above. To note, in case of early discontinuation of follow-up, time to event analysis to derive the -days mortality rate will be applied, censoring such subjects at their last valid observation date.

All secondary endpoints analyses will be based on mITT population and PP population and undergo the same sensitivity analyses as the primary analysis, as applicable.

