#### **7.4.1.5 Compassionate Use Experience**

Under compassionate exemption, 7 patients with severe COVID-19 infections have been treated with opaganib. These results are uncontrolled however provide important clinical data within the compassionate use context. One patient improved 36 hours after initiation of treatment to room air and was discharged from hospital. Five other patients were treated with opaganib for up to 14 days. All patients had clinical improvement and were discharged from hospital. Patients treated with opaganib in the compassionate use program did not progress to requiring intubation and mechanical ventilation. Patients receiving opaganib via compassionate use were compared to a matched case-control group of 18 patients (Kurd, 2020). Opaganib treated patients had faster improvement in lymphocyte counts, decreased CRP and faster time to being weaned off high flow oxygen. Of the 18 match controls, 6/18 cases required intubation and mechanical ventilation.

One patient started hydroxychloroquine, azithromycin and opaganib within 24 hours and had diarrhea necessitating withdrawal of all three medications. This was the only adverse event thought to be at least possibly related to opaganib.

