### 15.2 Secondary

- 1) The percentage of patients with  $\geq 2$  category improvement on the WHO Ordinal Scale for Clinical Improvement by Day 14 for the opaganib arm as compared to the placebo arm
- 2) Time to recovery as defined by improvement to a score of 3 or less on the WHO Ordinal Scale for Clinical Improvement for the opaganib arm as compared to the placebo arm
- 3) Time to low oxygen flow via nasal cannula e.g. from high oxygen flow via nasal cannula or positive pressure ventilation at baseline
- 4) The time to discharge from the hospital for the opaganib arm as compared to the placebo arm
- 5) The percentage of patients requiring intubation and mechanical ventilation by day 42 for the opaganib arm as compared to the placebo arm
- 6) The time to two consecutive negative swabs for SARS-CoV-2 by PCR, at least 24 hours apart for the opaganib arm as compared to the placebo arm
- 7) The percentage of patients with at least two consecutive negative swabs for SARS-CoV-2 by PCR at Day 14 for the opaganib arm as compared to the placebo arm
- 8) The percentage of patients with at least one measurement of fever at baseline (defined as temperature  $>38.0$  C [100.4 F]), who are afebrile (defined as temperature  $<37.2$  C [99 F]) at Day 14 for the opaganib arm as compared to the placebo arm
- 9) Mortality due to any cause at Days 28 and 42 after baseline for the opaganib arm as compared to the placebo arm

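### Intubation by Day 42: a single dropout turns the percentage of patients intubated into a death-censored probability, which is a different quantity

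*Protocol*

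**What the plan says.** Protocol Section 15.2 defines secondary endpoint 5 as "The percentage of patients requiring intubation and mechanical ventilation by day 42", compared between arms. Section 19.5 then sets the analysis:

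- **First choice:** "this endpoint is aimed to be assessed as a binary endpoint analysis, unless there are subjects who discontinue the study before meeting event of interest".
- **Fallback:** a Day-42 cumulative incidence from a time-to-event analysis, with dropouts censored at their last valid observation. For deaths, "Death prior to experiencing this progression-type of event will be handled via censoring at date of death".
- **Reason given:** mortality is a separate secondary endpoint, so "this approach to handling death would allow assessing the effect of opaganib specifically on this event".
- **Sensitivity:** "Sensitivity analysis will estimate cumulative incidence using the nonparametric Aalen-Johansen estimator, where death is a competing event".

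For improvement-type binary endpoints the same section uses another rule: "death before event of interest will be censored at timeframe end, thus taking the highest unfavorable possible outcome for the endpoint".

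Section 19.5 does not name the estimator for the intubation fallback. I read it as one minus Kaplan-Meier (1-KM), for two reasons: the section's general text on time-to-event endpoints says "Kaplan-Meier plot by treatment arm will be presented and cumulative incidence of events of interest will be estimated", and Aalen-Johansen is set apart as the alternative.

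**The concern.** The two branches do not estimate the same thing. In the binary analysis a patient who dies unintubated stays in the denominator as not intubated, so the result is the stated percentage. In the fallback that patient is censored, and the method lets those still at risk stand in for the dead. The result is the risk of intubation in a setting without death.

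Which of the two is reported depends on whether at least one patient discontinues before the event, which has nothing to do with the clinical question. The fallback figure is never below the competing-risk percentage, and its excess depends on how many patients in that arm die unintubated and when. Arms with equal percentages intubated can therefore show a difference.

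The improvement endpoints avoid this. Censoring death at the end of the timeframe keeps the dead in the denominator, so the dropout fallback still targets a percentage of patients.

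**Working it through.** **Inputs.** The protocol gives 464 patients, 1:1 (Section 19.1). It has no design calculation for this endpoint to reproduce and no rate of death without intubation. Its only intubation figure is "6/18 cases required intubation and mechanical ventilation", that is 33%, in matched controls of the compassionate-use series (Section 7.4.1.5). The rates below are therefore assumptions, shown over a range.

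**1. How likely is the switch?** With a probability p that a patient discontinues before the event, independently between patients, P(at least one) = 1 − (1 − p)^464.

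| p | P(at least one) |
|---|---|
| 0.1% | 37% |
| 0.5% | 90% |
| 1% | 99% |

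**2. How far does the figure move?** Let I be the true proportion intubated by Day 42 and D the proportion dying unintubated. With constant cause-specific hazards, the cumulative intubation hazard is

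hI = −ln(1 − I − D) × I/(I + D), and 1-KM = 1 − exp(−hI).

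For I = 0.30, D = 0.15: −ln(0.55) = 0.598; × 0.30/0.45 = 0.399; 1 − exp(−0.399) = 0.329.

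| I (actual) | D | 1-KM | Excess, points |
|---|---|---|---|
| 10% | 2% | 10.1% | 0.1 |
| 20% | 5% | 20.6% | 0.6 |
| 30% | 5% | 30.9% | 0.9 |
| 30% | 15% | 32.9% | 2.9 |
| 33% | 15% | 36.2% | 3.2 |
| 30% | 20% | 34.0% | 4.0 |

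**3. Does this rest on constant hazards?** The direction does not; the size does. If all unintubated deaths come after all intubations, the excess is zero. If all come before, 1-KM = I/(1 − D). For 30% and 15% that is 0.30/0.85 = 35.3%, so timing alone gives a range of 30.0% to 35.3%.

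**4. Is it the dropout or the censoring of deaths?** In 4,000 simulated arms of 232 patients (30% intubated, 15% dead unintubated, one event-free patient lost at Day 20), the means were 30.0% for the simple proportion, 30.1% for Aalen-Johansen and 33.0% for 1-KM. The dropout moves the estimate by about 0.1 point; censoring the deaths moves it by a further 2.9. In a single worked arm of 232 (46 intubated, 23 dead unintubated, one lost at Day 20), the simple proportion is 19.8%, 1-KM is 20.7%, and carrying the deaths as non-events to Day 42 gives 19.9%.

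**5. Between arms.**
- Equal intubation of 30%, unintubated deaths 5% against 15%: the fallback gives 30.9% against 32.9%, a 2.0-point difference where none exists.
- Equal intubation of 20%, deaths 5% against 10%: a spurious difference of 0.6 points.
- Equal intubation *hazards* (hI = −ln 0.70 in both arms), deaths 10% against 20%: the fallback gives 30% in both arms, while Aalen-Johansen gives 28.3% against 26.5%. The arm with more deaths now looks better. Adding the deaths gives intubation or death of 38.3% against 46.5%.

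**The case against.** The strongest reply is that the choice is deliberate. Section 19.5 gives its reason, mortality is assessed separately, and the Aalen-Johansen figure will be reported anyway. A different rule for a progression-type event is also defensible. Censoring death at the end of the timeframe is the worst outcome for a recovery endpoint but the best one for intubation. The last example above shows the price of Aalen-Johansen: when intubation hazards are equal, it favours the arm with more deaths, while the planned figure correctly shows no effect on intubation.

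The size is probably modest too. Section 11.2 excludes patients with do-not-intubate or do-not-resuscitate orders and those judged unlikely to survive 72 hours, which should make unintubated death less common. With 232 per arm at 30%, the 95% interval for a difference is about ±8.3 points (1.96 × √(2 × 0.30 × 0.70/232)). The endpoint is secondary and tested hierarchically (Section 19.7), and the estimator is inferred rather than named.

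These points limit the size and seriousness of the problem. They do not remove it. The stated reason supports a cause-specific hazard comparison. It does not support presenting a death-censored probability as the percentage of patients intubated. Nor does it explain why the target should change only when someone drops out: if isolating intubation were the aim, it would apply without dropout as well. The weakness of Aalen-Johansen is real, and the fix has to address it.

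**Conclusion.** The concern holds. Section 19.5 lets a single pre-event dropout replace the stated percentage with a different quantity, and the switch is close to certain at any ordinary dropout rate. Under the assumed rates and constant hazards the overstatement is 0.1 to 4.0 points per arm. The spurious difference between arms reaches 2.0 points in the scenarios tried, and that case needs a threefold imbalance in unintubated deaths. If such deaths are rare (2% to 5%), the excess is 0.1 to 0.9 points.

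The sizes rest on assumed rates, because the protocol gives none for death without intubation, and on reading the fallback as 1-KM. No effect on the hierarchical p-value is claimed, since Section 19.5 does not name the test for this branch. The primary endpoint is not affected. The change is worth making because it is cheap and fixes what the endpoint measures before the data are seen.

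**What to change.** In Section 19.5:

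1. Make the Aalen-Johansen estimate at Day 42 (death as a competing event, dropouts censored) the main percentage for this endpoint, with its between-arm difference and 95% confidence interval, whether or not anyone drops out. Without dropout it equals the simple proportion, so the switch disappears.
2. Keep the death-censored analysis as supportive, and label it a cause-specific hazard comparison. That serves the stated rationale.
3. Report intubation or death by Day 42 by arm beside the main estimate, because deaths before intubation lower the Aalen-Johansen figure. It is not among the Section 15.2 endpoints, so describe it as supportive and leave the testing order unchanged.

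The cost is a wording change, a stated method for the difference and its interval, and one added summary. The intubation, death and last-observation dates are the ones the planned analysis already needs.
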